8.2 Background Characteristics

8.2.1 Subject Disposition

A disposition table will be provided for the Run-in Period with the following categories:

- All Subjects Set
- Safety Set for the Run-in Period

The number and percentage (based on the Safety Set for the Run-in Period) of subjects in each of the following disposition categories will be summarized:

- Completed Run-in Period treatment
- Prematurely discontinued Run-in Period treatment and the reason for treatment discontinuation
- Prematurely discontinued study in the Run-in Period and the reason for study discontinuation

A separate disposition table will be provided for the Treatment Period with the following categories:

- Randomized
- Safety Set for the Treatment Period
- Full Analysis Set (FAS)
- Randomized but not dosed

The number and percentage (based on the FAS) of subjects in each of the following disposition categories will be summarized by treatment group and overall:

- Completed treatment
- Prematurely discontinued treatment and the reason for discontinuation
- Completed study
- Prematurely discontinued study and the reason for discontinuation
- Rollover to open-label extension study

A listing will be provided for subjects who discontinued treatment (including both the Run-in Period and the Treatment Period) or who discontinued study with reasons for discontinuation.

8.2.2 Demographics and Baseline Characteristics

Demographics and baseline characteristics will be summarized by treatment group and overall based on the FAS.

Demographic data will include the following:

- Age at Day 1 (in years)
- Sex (male; female)
- Ethnicity (Hispanic or Latino; Not Hispanic or Latino; Not Collected per Local Regulations)
- Race (White; Black or African American; Northeast Asian; Southeast Asian; Other Asian; Asian (Region Not Reported); American Indian or Alaska Native; Native Hawaiian or Other Pacific Islander; Other; Multiracial; Not Collected per Local Regulations)
- Geographic region (North America [including United States]; Rest of the World [including Europe, Israel, Australia, and New Zealand])

Baseline characteristics will include the following:

- Weight (kg)
- Height (cm)
- BMI (kg/m²)
- BMI z-score (for subjects ≤ 20 years old at Baseline)

Stratification categories will include the following:

- Age at the Screening Visit (< 18 ; ≥ 18 years)

- ppFEV₁ at Day -14 (<70; ≥70 percentage points)
- SwCl at Day -14 (<30; ≥30 mmol/L)
- Prior CFTR modulator Use (Yes; No)

Disease characteristics will include the following:

- ppFEV₁ at baseline (<40; ≥ 40 to <70; ≥70 to ≤90; >90 percentage points)
- ppFEV₁ at baseline (continuous)
- Sweat chloride at baseline (<30; ≥30 to <60; ≥60 mmol/L)
- Sweat chloride at baseline (continuous)
- CFQ-R respiratory domain score at baseline (adult and child version only) (continuous)
- Prior use of dornase alfa before first dose of study drug in the Treatment Period (Yes; No)
- Prior use of azithromycin before first dose of study drug in the Treatment Period (Yes; No)
- Prior use of inhaled antibiotic before first dose of study drug in the Treatment Period (Yes; No)
- Prior use of any bronchodilator before first dose of study drug in the Treatment Period (Yes; No)
- Prior use of inhaled hypertonic saline before first dose of study drug in the Treatment Period (Yes; No)
- Infection with *Pseudomonas aeruginosa* within 2 years prior to screening (Positive; Negative)

In addition, data listings will also be provided for:

- Informed consent
- Inclusion/exclusion criteria violation for subjects with any such violations

8.2.3 Medical History

Medical history will be coded using the Medical Dictionary for Regulatory Activities (MedDRA). For the FAS, medical history will be summarized descriptively by System Organ Class (SOC) and Preferred Term (PT). This summary will be provided by treatment group and overall. The corresponding data listing will also be provided.

In addition, the number of subjects reported to have had positive cultures for respiratory pathogens within the 2 years prior to screening (i.e., answered yes on the respiratory microbiology form) will be summarized by treatment group and overall for the FAS. The corresponding data listing will be provided.

8.2.4 Prior and Concomitant Medications

Medications will be coded using the World Health Organization Drug Dictionary (WHODrug) and categorized as follows:

Prior medication: any medication that was administered during the 56 days before the first dose of study drug in the Treatment Period excluding the ones that started in the Run-in Period. For subjects who discontinue during the Run-in Period and whose first dose of study drug in the Treatment Period is not available, prior medication will be any medication that was administered during the 56 days before the last dose of study drug in the Run-in Period excluding the ones that started after the first dose in the Run-in Period.

Concomitant medication during the Run-in Period: medication continued or newly received during the TE Period for the Run-in Period

Concomitant medication during the Treatment Period: medication continued or newly received during the TE Period for the Treatment Period

Post-treatment medication: medication continued or newly received after:

- the TE Period for the Run-in Period if the subject did not receive study drug in the Treatment Period
- the TE Period for the Treatment Period for subjects who received study drug in the Treatment Period

A given medication may be classified as any combination of the above categories: for example, prior and concomitant during the Run-in Period, concomitant during the Treatment Period and post-treatment, or concomitant for both periods and post-treatment.

If a medication has a completely missing or partially missing start/stop date and if it cannot be determined whether it was taken before the first dose date of study drug, concomitantly, or after the TE Period, it will be classified as prior, concomitant for both periods, and post-treatment. Details for imputing missing or partial start and/or stop dates of medication are described in [Appendix](#).

Prior medications and concomitant medications will be summarized descriptively for the FAS using frequency tables by: 1) treatment group and overall, Preferred Name (PN); and 2) treatment group and overall, Anatomical Therapeutic Chemical class (ATC) level 1, ATC level 2, and PN.

Prior medications and concomitant medications during the Run-in Period will be summarized together in one summary table. Post-treatment medications will be listed in the all medications listing.

8.2.5 Study Drug Exposure

Study drug exposure will be summarized by treatment group and overall for the Treatment Period only based on the Safety Set for the Treatment Period.

Duration of study drug exposure (in days) will be calculated as: last dose date of study drug during the Treatment Period – first dose date of study drug during the Treatment Period + 1, regardless of study drug interruption.

Study drug exposure (in weeks) will be summarized descriptively by the number of subjects (n), mean, SD, median, min, and max. It will also be summarized by interval (≤ 1 week; >1 to ≤ 2 weeks; >2 to ≤ 4 weeks; >4 to ≤ 12 weeks; >12 to ≤ 24 weeks; >24 to ≤ 36 weeks; >36 to ≤ 52 weeks; >52 weeks) using counts and percentages. Additionally, the total study drug exposure,

defined as the sum total of the study drug exposure across all subjects (in patient-weeks and patient-years), will be provided.

8.2.6 Study Drug Compliance

Study drug compliance will be summarized by treatment group and overall for the Treatment Period only based on the FAS.

Study drug compliance will be calculated as: $100 \times [1 - (\text{total number of days of study drug interruption during the Treatment Period}) / (\text{duration of study drug exposure in days during the Treatment Period})]$. A study drug interruption on a given day is defined as an interruption of any study drug on that day.

Percentage of study drug compliance will be summarized descriptively by the number of subjects (n), mean, SD, median, min, and max. It will also be summarized in categories (<80%; ≥80%) using frequency tables.

8.2.7 Important Protocol Deviations

An important protocol deviation (IPD) is a deviation that may significantly impact the completeness, accuracy, or reliability of key study data or that may significantly affect a subject's rights, safety or well-being. IPDs will be identified by the PD review team according to the protocol deviation plan which will be finalized before the database lock.

IPDs will be summarized descriptively based on the FAS and presented by treatment group and overall. Additionally, IPDs will be provided in an individual subject data listing.

8.3 Efficacy Analysis

All efficacy analyses described in this section will be based on the FAS, unless otherwise specified. The analysis of the below secondary endpoints will be performed based on the PFAS in order to increase the power for the analyses:

- Proportion of subjects with SwCl <60 mmol/L through Week 24 (pooled with data from Study 103)
- Proportion of subjects with SwCl <30 mmol/L through Week 24 (pooled with data from Study 103)

The primary and key secondary endpoints will be formally tested for statistical significance, and the tests will be subject to multiplicity control (see 8.3.2.3 for details). The endpoints involving ppFEV₁ and SwCl which are not primary or key secondary will be supportive and analyzed similarly to the corresponding primary and key secondary endpoints; the *P* value presented will be nominal.

8.3.1 Analysis of Primary Efficacy Variable

8.3.1.1 Definition of Primary Efficacy Variable

The primary efficacy variable is the absolute change from baseline in ppFEV₁ through Week 24 (estimated by averaging Weeks 16 and 24). Percent predicted FEV₁ is the ratio of observed FEV₁ (L) and predicted FEV₁ (L), expressed as a percentage. See [Appendix](#) for more details.

8.3.1.2 Definition of Primary Estimand

The primary estimand is defined as the following and is presented in [Appendix](#) :

- Treatment: VNZ/TEZ/D-IVA versus ELX/TEZ/IVA
- Population: Study population represented by inclusion and exclusion criteria
- Variable: Absolute change from baseline (after ELX/TEZ/IVA run-in) in ppFEV₁ through Week 24 (estimated by averaging Weeks 16 and 24)
- Handling of intercurrent events (ICE):
 - o The treatment policy strategy will be used to handle the use of non-study drug CFTR modulators for >3 days in either the Run-in Period or the Treatment Period prior to Week 24, which means that observed ppFEV₁ values will be used, if available, after this prohibited medication use.
 - o The treatment policy strategy will be used to handle treatment discontinuation prior to Week 24, which means that observed ppFEV₁ values will be used, if available, after treatment discontinuation.
- Population level summary: Difference in variable means between VNZ/TEZ/D-IVA and ELX/TEZ/IVA groups

8.3.1.3 Primary Analysis

The primary null hypothesis to be tested is that the mean for the primary efficacy variable for VNZ/TEZ/D-IVA is inferior by >3 percentage points compared to ELX/TEZ/IVA. The primary analysis of the primary estimand will be performed using a mixed-effects model for repeated measures (MMRM) with change from baseline at Day 15, Week 4, Week 8, Week 16, and Week 24 as the dependent variable. The model will include fixed categorical effects for treatment, visit, age at screening (<18 versus ≥18 years of age), and treatment-by-visit interaction, with baseline ppFEV₁ and baseline SwCl as continuous covariates. The model will be estimated using restricted maximum likelihood. Denominator degrees of freedom for the *F*-test for fixed effects will be estimated using the Kenward-Roger approximation⁵. An unstructured covariance structure will be used to model the within-subject errors. If the model estimation does not converge, an alternative covariance structure like compound symmetry will be used. Conditional on the observed data and covariates, missing data will be assumed to be missing at random (MAR).

The primary result obtained from the model will be the estimated treatment difference through Week 24 (estimated by averaging Weeks 16 and 24). The adjusted mean with a 2-sided 95% CI and the 1-sided *P* value for non-inferiority will be provided. The primary null hypothesis will be rejected, and non-inferiority demonstrated, if the lower bound of the CI is ≥-3.0.

The primary null hypothesis of non-inferiority described above will be tested based on the FAS.

If non-inferiority for the primary endpoint is demonstrated, and if the lower bound of the same 95% CI is greater than 0, then superiority for the primary endpoint is also demonstrated, and the 2-sided *P* value for superiority will be presented.

The estimated within-group change from baseline and treatment difference at each post-baseline visit, obtained from the model, will be provided. The estimated within-group change and its standard error (SE) at each post-baseline visit will also be plotted by treatment group.

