## 9.2 Method of Assigning Subjects to Treatment Groups

Subjects will be randomized (1:1) to the VX-121/TEZ/D-IVA group or the ELX/TEZ/IVA group. Randomization will be stratified by age at the Screening Visit (<18 versus  $\geq$ 18 years of age), ppFEV1 determined during the Run-in Period (Day -14 clinic assessment; <70 versus  $\geq$ 70), SwCl determined during the Run-in Period (Day -14 assessment; <30 versus  $\geq$ 30 mmol/L), and prior CFTR modulator use (yes versus no). If the Day -14 ppFEV1 and/or SwCl values are not valid or not available, the most recent available clinic-assessed ppFEV1 and/or SwCl value will be used for stratification.

An interactive web response system (IWRS) will be used to assign subjects to treatment. The randomization code list will be produced by Vertex Biometrics or a qualified randomization vendor.

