##### **12.3.3.1 Analysis of Primary Endpoint**

The primary efficacy endpoint is the absolute change from baseline in ppFEV1 through Week 24 (estimated by averaging Weeks 16 and 24). The primary analysis will be conducted with clinic spirometry data only and will be performed using a mixed-effects model for repeated measures

(MMRM) with absolute change from baseline in ppFEV1 at Day 15, Week 4, Week 8, Week 16, and Week 24 as the dependent variable. The model will include treatment group, visit, and treatment-by-visit interaction as fixed effects, with continuous baseline ppFEV1, continuous baseline SwCl, and age at screening (<18 versus ≥18 years of age) as covariates. The model will be estimated using restricted maximum likelihood. Denominator degrees of freedom for the F test for fixed effects will be estimated using the Kenward-Roger approximation. An unstructured covariance structure will be used to model the within-subject errors. If the model estimation does not converge, a compound symmetry covariance structure will be used instead. Conditional on the observed data and covariates, missing data will be assumed to be missing at random; therefore, no imputation of missing data will be performed.

The primary result obtained from the model will be the estimated treatment difference through Week 24. The adjusted mean with a 2-sided 95% CI will be provided. The primary null hypothesis will be rejected and non-inferiority demonstrated if the lower bound of the 95% CI is ≥-3.0. The estimated within group change from baseline and the treatment difference at each post-baseline visit will also be provided, obtained from the model.

The primary null hypothesis of non-inferiority described above will be tested based on the FAS. If the lower bound of the 95% CI is greater than 0, then superiority for the primary endpoint is demonstrated and the 2-sided *P* value for superiority will be calculated.

Sensitivity analyses for handling missing data will be described in the SAP.

Supportive analyses and subgroup analyses (as appropriate) will also be described in the SAP.

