6.3 Randomization

Approximately 400 subjects will be randomized (1:1) to the VNZ/TEZ/D-IVA group or the ELX/TEZ/IVA group. Randomization will be stratified by age at the Screening Visit (<18 versus ≥18 years of age), ppFEV₁ determined during the Run-in Period (Day -14 clinic assessment; <70 versus ≥70 percentage points), SwCl determined during the Run-in Period (Day -14 assessment; <30 versus ≥30 mmol/L), and prior CFTR modulator use (yes versus no).

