8.3.2.2 Analysis Method

Absolute change from baseline in SwCl through Week 24:

The estimand for the absolute change from baseline (after ELX/TEZ/IVA run-in) in SwCl through Week 24 is defined as the following:

- Treatment: VNZ/TEZ/D-IVA versus ELX/TEZ/IVA
- Population: Study population represented by inclusion and exclusion criteria
- Variable: Absolute change from baseline in SwCl through Week 24 (estimated by averaging Weeks 16 and 24)
- Handling of ICE: Same as the primary estimand (8.3.1.2)
- Population level summary: Difference in variable means between VNZ/TEZ/D-IVA and ELX/TEZ/IVA groups

The analysis of absolute change from baseline in SwCl through Week 24 will be based on an MMRM similar to the primary analysis of the primary estimand (8.3.1.3), with absolute change from baseline in SwCl at Day 15, Week 4, Week 16, and Week 24 as the dependent variable. The estimated treatment difference through Week 24 (estimated by averaging Weeks 16 and 24) will be presented along with the 2-sided 95% CI and *P* value. The estimated within-group change from baseline and treatment difference at each post-baseline visit, obtained from the model, will be provided. The estimated within-group change and its SE at each post-baseline visit will also be plotted by treatment group.

Proportion of subjects with SwCl <60 mmol/L through Week 24 (pooled with data from Study 103):

The estimand for the proportion of subjects with SwCl <60 mmol/L through Week 24 is defined as the following:

- Treatment: VNZ/TEZ/D-IVA versus ELX/TEZ/IVA
- Population: Pooled study population represented by inclusion and exclusion criteria
- Variable: Response defined as SwCl <60 mmol/L through Week 24 (estimated by averaging Weeks 16 and 24)
- Handling of ICE: Same as the primary estimand (8.3.1.2)
- Population level summary: Odds ratio comparing the response rates in VNZ/TEZ/D-IVA and ELX/TEZ/IVA groups

The response corresponding to SwCl <60 mmol/L at each visit through Week 24 in the PFAS will be analyzed using a generalized estimating equations (GEE) model. The model will include fixed categorical effects for treatment, age at screening (<18 versus ≥18 years of age), genotype group (F/MF, F/F, F/G, F/RF, TCR/non-F), visit, and treatment-by-visit interaction, with baseline ppFEV₁ and baseline SwCl as continuous covariates. A logit link function and an unstructured working correlation matrix will be used in the GEE model. If the model estimation

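### Prior CFTR modulator use stratifies randomisation but has no term in the ppFEV1 or SwCl MMRM, so the standard error is slightly too wide if the factor is prognostic

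*SAP*

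**What the plan says.** SAP 6.3 stratifies randomisation by four factors. Three of them are age group at screening (under 18 versus 18 or older), Day -14 ppFEV1 (below 70 versus 70 or more) and Day -14 SwCl (below 30 versus 30 mmol/L or more). The fourth is given as "and prior CFTR modulator use (yes versus no"). Protocol 9.2 lists the same four factors.

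For the primary analysis, SAP 8.3.1.3 states: "The model will include fixed categorical effects for treatment, visit, age at screening". It adds the treatment-by-visit interaction and continuous baseline ppFEV1 and SwCl. Protocol 12.3.3.1 has the same content: "The model will include treatment group, visit, and treatment-by-visit interaction as fixed effects", with baseline ppFEV1, baseline SwCl and age group as covariates.

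The first key secondary analysis, change in SwCl, is "based on an MMRM similar to the primary analysis of the primary estimand (8.3.1.3), with absolute change from baseline in SwCl" as the outcome (SAP 8.3.2.2). No further covariate is named there.

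In the SAP's analyses the fourth factor appears only as a row of the baseline table, "Prior CFTR modulator Use (Yes; No" (SAP 8.2.2). It is not among the subgroups in 8.3.1.5, no sensitivity analysis uses it, and neither document says why it was left out.

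**The concern.** Stratified allocation balances a factor between arms, so chance imbalance in it no longer adds to the variance of the treatment difference. A model without the factor does not know this. It leaves the factor's variance in the residual and reports a standard error larger than the true one. The same 95% interval decides both non-inferiority and superiority for ppFEV1, and SwCl is the first test after it in the hierarchy. Unneeded width could matter for a superiority or SwCl result near its boundary.

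Residual prognostic value is plausible from the design. Under Protocol 9.5, subjects already on a Vertex modulator may enter the run-in without washout. A subject with no prior modulator use starts ELX/TEZ/IVA at Day -28, so the Day 1 baseline follows only about four weeks of treatment. The SwCl baseline averages the two most recent pre-dose values from Day -14 onward (SAP 8.1), so it can include a value taken about two weeks after starting. Two subjects with the same baseline could therefore differ in later change according to prior use.

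**Working it through.** **Inputs.** From SAP 6.2.1: SD 8, margin 3, true difference 0, one-sided alpha 0.025, 200 per arm, 10% drop-out. From SAP 6.2.2: SD 14 mmol/L, difference 5 mmol/L, two-sided alpha 0.05, same size and drop-out. Evaluable per arm: 200 × 0.9 = 180.

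**The plan's own figures.** SE = SD × √(2/180), which is 0.843 for ppFEV1 and 1.476 for SwCl.
- ppFEV1 power: Φ(3/0.843 − 1.96) = 94.5% (94.4% with the t distribution).
- SwCl power: Φ(5/1.476 − 1.96) = 92.3% (92.2% with t).

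Both agree with the stated figure of more than 90%.

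**Effect of the omission.** Let R² be the share of the residual variance, after the existing covariates, that prior modulator use explains. The documents do not give it; the range 0 to 10% is an assumption. Under stratified randomisation:
- SE with the term: SE × √(1 − R²)
- Overstatement without it: 1/√(1 − R²) − 1
- Actual one-sided alpha without it: 1 − Φ(1.96/√(1 − R²))
- Power without it: Φ((3 − 1.96 × 0.843)/(0.843 × √(1 − R²)))
- Power with it: Φ(3/(0.843 × √(1 − R²)) − 1.96)

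| ppFEV1 | R² = 0 | R² = 5% | R² = 10% |
|---|---|---|---|
| SE overstated by | 0% | 2.6% | 5.4% |
| CI half-width with the term | 1.653 | 1.611 | 1.568 |
| One-sided alpha without the term | 0.0250 | 0.0222 | 0.0194 |
| Power without the term | 94.5% | 94.9% | 95.4% |
| Power with the term | 94.5% | 95.4% | 96.3% |

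For SwCl at R² = 10%, the half-width falls from 2.89 to 2.74 mmol/L, and power is 93.4% without the term and 94.6% with it.

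**What the range means in ppFEV1 points.** If a proportion p of subjects is in one level and the levels differ by b points in mean change, R² = p(1 − p)b²/SD². With p = 0.8, b = 1, 2, 3 and 4 points overstate the SE by 0.1%, 0.5%, 1.1% and 2.1%. With p = 0.5 and b = 4 (R² = 6.3%) the figure is 3.3%. Reaching R² = 10% needs b = 8 × √(0.10/0.25) = 5.1 points at p = 0.5, or 8 × √(0.10/0.16) = 6.3 points at p = 0.8.

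**Simulation check.** 20,000 trials per setting, 360 evaluable subjects, permuted blocks within all four strata, 20% assumed in one level, and a complete-data ANCOVA standing in for the MMRM. At R² = 10% and a true difference of −3:
- Without the term: mean reported SE 0.844, actual SD of the estimate 0.807, false non-inferiority 2.1%.
- With the term: mean reported SE 0.801, actual SD 0.804, false non-inferiority 2.6%, within Monte Carlo error of 2.5%.

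The estimate itself is almost equally precise with or without the term (0.804 against 0.807). What the term mainly corrects is the reported SE.

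**The case against.** The strongest reply is that nothing here is invalid. The error is conservative, the loss falls on the sponsor, power holds, and the gain is zero if the factor is not prognostic. That is all true.

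The upper end of the range is also demanding. An R² of 10% needs a residual effect of 5 to 6 points, about twice the margin, that remains after baseline ppFEV1, baseline SwCl and age. The four-week run-in (Protocol 9.1.2) is meant to give every subject an on-treatment baseline, which makes a large residual effect less likely. This stands as a reason to expect the lower part of the range, about 0 to 3% on the ppFEV1 SE for effects up to 4 points. It does not show that the effect is nil, because a subject with no prior modulator use has only about four weeks of treatment at baseline.

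The SD of 8 is stated for a two-sample t-test without covariates. If the existing covariates already explain some variance, the absolute half-widths and gains above are too large. The percentage overstatement for a given R² is unaffected.

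Finally, the protocol fixes the same covariate list, so a change in the SAP alone would leave the two documents at odds. That is a documentation step and does not argue against the change. The covariate list is consistent across the documents, but this does not explain why one stratum is missing.

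**Conclusion.** The concern holds. Prior CFTR modulator use is the only stratification factor not represented in the primary MMRM. The SwCl MMRM shares the omission, on the reading that a model described as similar carries the same covariates.

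The consequence is small and in the conservative direction: an SE overstated by 0 to 5.4% if the factor explains 0 to 10% of residual variance, actual one-sided alpha between 0.025 and about 0.019 to 0.021, and a power gain of at most about 1 point. There is no bias, no inflation of type I error and no threat to the stated power. The size depends on the factor's prevalence and residual prognostic strength, neither of which the documents give. This is a cheap improvement that should be made, not the repair of an invalid analysis.

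**What to change.** Before database lock, add prior CFTR modulator use (yes/no, as used for stratification) as a fixed categorical effect in the ppFEV1 MMRM (SAP 8.3.1.3), the SwCl MMRM (8.3.2.2) and the MMRMs built on them (8.3.1.4, 8.3.3.2, 8.3.4.2).

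Record the departure from Protocol 12.3.3.1 and the synopsis in SAP 2.1, which now reads as not applicable. State in 8.3.1.5 whether the term carries into the subgroup fits, where one level may be sparse. The subgroup list itself need not change.

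No change is asked of the GEE models for the SwCl thresholds. In a logit model an added covariate changes the odds ratio being estimated, and the documents do not give Study 103's stratification factors.

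The cost is one degree of freedom, one term in existing code and a short SAP entry; the variable is already collected and tabulated. A pre-specified sensitivity analysis with the term, or a stated reason for leaving it out, would be a weaker but acceptable answer.
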